7.3.4 Physical and functional performances

- **Hand-grip strength:** Measured using a calibrated hand dynamometer from the American Society of Hand Therapists (ASHT) protocol:
 - Seated position, shoulder adducted/neutral rotation, elbow 90° flexion, forearm neutral, wrist 0–30° dorsiflexion, and 0–15° ulnar deviation.
 - Feet flat on floor, dry hands.
 - Three maximal efforts on the dominant hand with 30-second rest; the highest value recorded (kg).
 - Procedure terminated if pain or discomfort is reported.
- **Gait speed:** 6-meter walk test:
 - 10-meter straight pathway marked at 0, 2, 6, 8, and 10 meters (2m acceleration, 6m timed, 2m deceleration).
 - Usual walking pace, no running, assistive device allowed if habitual.
 - Two trials; time recorded from 2m to 8m mark; average speed (m/s) calculated.
- **Frailty status:** Cardiovascular Health Study (CHS) criteria:
 - Unintentional weight loss (>4.5 kg or >5% in past year).
 - Weakness (grip strength lowest quintile by sex/BMI).
 - Exhaustion (self-reported).
 - Slowness (gait speed lowest quintile by sex/height).
 - Low physical activity (weighted score of kcal/week).
 - Scoring: 0 = robust, 1–2 = pre-frail, ≥3 = frail.
- **Instrumental Activities of Daily Living (IADL):** Lawton scale (score >5 required at inclusion; monitored for changes).

7.3.5 Cognitive and psychological assessments

- Montreal Cognitive Assessment Indonesian version (MoCA-Ina): Administered face-to-face by trained assessor; total score 0–30 (education adjustment: +1 if ≤12 years formal education).
- Geriatric Depression Scale-15 (GDS-15): Self-reported or interviewer-assisted.
- De Jong Gierveld Loneliness Scale (Indonesian version): 11-item questionnaire.
- Physical Activity Scale for the Elderly (PASE): Interviewer-administered; converted frequency and duration scores.

7.3.6 Health-related quality of life and comorbidity

- Short Form-12 (SF-12): Physical and mental component summaries.
- EQ-5D-5L: 5 domains (mobility, self-care, usual activities, pain/discomfort, anxiety/depression) plus visual analog scale.
- Charlson Comorbidity Index (CCI): Calculated from medical history and records.

7.3.7 Intervention-specific procedures

- Nutritional education (both groups):
 - Tele-conference consultations (Zoom): Personalized meal planning by dietitian.
 - E-fliers: Digital delivery with confirmation of receipt.
- Structured exercise (intervention group):
 - Pre-session screening: Symptom query, vital signs if needed.

- Session monitoring: Borg Rating of Perceived Exertion scale; termination if excessive dyspnea, pain, dizziness, or hemodynamic changes.
- Intergenerational activities (intervention group):
 - Pre-session preparation: Facility check (seating, materials, spacing).
 - Session structure: Introduction, AMIR-based activities (comic reading, joint gymnastics, games), reflection.
 - Post-session: Brief feedback from the elderly and children.

7.3.8 Monitoring and adherence

Adherence and safety are monitored proactively to maximize retention and minimize risks.

- Adherence monitoring:
 - Exercise sessions (intervention arm): Attendance logged by instructor and research assistant; session completion confirmed ($\geq 85\%$ of planned sessions required for per-protocol analysis).
 - Intergenerational activities: Attendance sheets signed by research team and orphanage staff; activity completion checklists.
 - Nutritional education (both arms): Confirmation of tele-conference attendance and e-flyer receipt/viewing (via read receipts or follow-up query).
 - Overall: Monthly telephone counseling (2–3 calls/month) by research team to encourage compliance, address barriers, and reinforce motivation.
- Safety monitoring:
 - During exercise phase: Weekly (Monday) pre-session symptom and condition checks by team/instructor; Borg Rating of Perceived Exertion scale monitored throughout sessions; immediate termination for excessive symptoms (severe dyspnea, palpitations, dizziness, heavy weakness, pre-syncope).
 - Bi-weekly direct evaluations (weeks 4, 6, 8, 10): Remote or in-person query on complaints, with direct supervision during selected sessions.
 - Intergenerational phase: On-site supervision by research team and orphanage staff; post-session brief feedback on comfort/discomfort.
 - General: Participants provided with contact number for immediate reporting; all potential adverse events (fatigue, muscle pain, emotional discomfort, minor injuries) documented, managed, and reported to Ethics Committee if serious.

7.3.9 Questionnaires

All questionnaires are administered by trained research assistants through structured interviews to ensure consistency, especially for participants with limited literacy or visual impairment. Questionnaires are completed at baseline (week 0), intermediate (week 12), and final (week 16) assessments unless otherwise specified. Validated Indonesian versions are used where available.

- **Short Form-12 (SF-12):** Measures health-related quality of life with 12 items covering physical and mental component summaries (PCS and MCS). Scores are calculated using standard algorithms (range 0–100; higher scores indicate better quality of life). Primary focus on changes in physical and mental health domains.

- **EQ-5D-5L (EuroQol 5 Domains – 5 Levels):** Assesses five dimensions (mobility, self-care, usual activities, pain/discomfort, anxiety/depression) with 5 response levels each, plus a visual analog scale (EQ-VAS) for overall health state (0–100). Utility scores are derived using Indonesian value sets if available.
- **Geriatric Depression Scale-15 (GDS-15):** Screens for depressive symptoms with 15 yes/no items (score range 0–15; ≥5 suggests depression). Used for monitoring psychological well-being and exclusion criteria confirmation.
- **De Jong Gierveld Loneliness Scale (Indonesian version):** 11-item scale measuring emotional and social loneliness (range 0–11; higher scores indicate greater loneliness). Helps evaluate the impact of social isolation and potential benefits from intergenerational activities.
- **Physical Activity Scale for the Elderly (PASE):** Assesses leisure, household, and occupational physical activity over the past week. Scores are calculated based on frequency, duration, and intensity weights (higher scores indicate greater activity level). Administered to monitor baseline activity and changes.
- **Mini Nutritional Assessment (MNA) – Full version:** 18-item tool including anthropometric measures, global assessment, dietetic assessment, and subjective items (maximum 30 points: ≥24 normal, 17–23.5 at risk, <17 malnourished). Complements nutritional education intervention.
- **Charlson Comorbidity Index (CCI):** Calculated from medical history (19 conditions weighted 1–6 points) to quantify comorbidity burden and adjust for confounding in analyses.

7.4 Study visits

Study visits are scheduled to minimize burden while ensuring complete data collection. Visits occur at community centers, participant homes (if needed), or orphanages.

- Screening/Baseline visit (week 0, 1–2 days):
 - Explanation of study, informed consent (elderly and orphanage for children).
 - Medical history, comorbidity assessment (CCI), medication review.
 - Full physical examination, vital signs, anthropometry.
 - Cognitive (MoCA-Ina), physical (hand-grip strength, gait speed), functional (IADL), frailty (CHS), nutritional (MNA), and psychological assessments.
 - All questionnaires (SF-12, EQ-5D-5L, GDS-15, PASE, loneliness scale).
 - Blood sampling.
 - Randomization (post-eligibility confirmation).
 - Nutritional education initiation (first tele-conference scheduling).

- Intermediate visit (end of week 12, post-exercise phase):
 - Repeat anthropometry, vital signs.
 - Physical performance (hand-grip strength, gait speed), frailty status.
 - Cognitive (MoCA-Ina) and selected questionnaires (SF-12, EQ-5D-5L, GDS-15, loneliness).
 - Blood sampling.
 - Adherence review; ToT preparation for SHP (intervention arm).
- Final visit (end of week 16):
 - Comprehensive repeat of baseline assessments (all physical, cognitive, functional, nutritional, psychological, and questionnaires).
 - Blood sampling.
 - Adherence summary, adverse event review.
 - Compensation distribution (transport reimbursement, snacks provision during study).
- Ongoing visits/activities:
 - Exercise: Weekly tele-sessions (intervention group).
 - Intergenerational: 8 in-person sessions at orphanages (weeks 13–16).
 - Nutritional: 2 tele-conferences + 5 e-flyers (both groups).
 - Monitoring calls.

Home visits arranged if mobility limits attendance.

7.5 Withdrawal of individual subjects

Participants (elderly or children via orphanage representative) may withdraw voluntarily at any time without providing reasons and without impact on routine care or relationship with researchers. Withdrawal is documented but no further study procedures performed unless consented for final assessment.

Investigator-initiated withdrawal occurs for:

- Development of exclusion criteria (e.g., new disability, dementia suspicion, uncontrolled chronic disease).
- Acute illness requiring hospitalization or prohibiting continuation (e.g., pneumonia, acute stroke, uncontrolled hypertension).
- Non-adherence (>3 consecutive missed exercise sessions or <85% overall intervention completion).
- Intolerable adverse events suspected related to intervention.

Withdrawn participants are encouraged to complete safety follow-up and/or final assessments for intention-to-treat analysis. All withdrawals are fully documented (reason, date, partial data

collected) and reported to Ethics Committee if related to safety. No replacement of withdrawn subjects.

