3. STUDY DESIGN

This is a single-center, randomized, open-label (unblinded), parallel-group controlled clinical trial evaluating the efficacy of a sequential multimodal intervention (structured physical exercise followed by SHP-based intergenerational activities) compared to nutritional education alone in community-dwelling elderly aged 60–75 years with physio-cognitive decline syndrome (PCDS).

The study duration per participant is 16 weeks, consisting of:

- Baseline assessment (week 0)
- Intervention period: 12 weeks of chair-exercise + 4 weeks of intergenerational activities (intervention arm) or continued education (control arm)
- Intermediate assessment (end of week 12)
- Final assessment (end of week 16)

Participants are randomized in a 1:1 ratio into two arms:

- Intervention arm (n=50): Nutritional education + 12 weeks structured chair-based exercise (PEROSI protocol, progressive frequency from 1 to 3 sessions/week, 60 minutes/session, supervised online) followed sequentially by 4 weeks SHP-based intergenerational activities (8 sessions, 2x/week, 45 minutes/session, paired 1:1 elderly-child using AMIR educational materials at selected orphanages).
- Control arm (n=50): Nutritional education only (2 personalized dietitian tele-conferences at weeks 1 and 11; 5 educational e-flyers at weeks 3, 5, 7, 13, and 15).

Randomization is computer-generated using permuted block randomization (block size 4), stratified if necessary, with allocation concealment managed by an independent third party. Blinding of participants and instructors is not feasible due to the nature of the behavioral interventions; however, outcome assessors for laboratory analyses (mBDNF) are blinded to group allocation where possible.

The trial follows intention-to-treat principles with per-protocol sensitivity analysis. Recruitment targets consecutive eligible elderly from community programs under the School of Medicine and Health Sciences at Atma Jaya Catholic University of Indonesia and the Archdiocese of Jakarta. Child participants (aged 5–8 years, n=50) are recruited from cooperating orphanages exclusively for the intervention arm.

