Participants in the control group will receive usual care according to existing community health services. They will not participate in the structured exercise or SHP-based intergenerational activities during the study period. However, they will continue to receive standard health education and routine activities available within their respective community settings.

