7.5.1 Drop out Criteria

Subjects are classified as drop-outs if they do not complete the study protocol through the final assessment (week 16) for any reason. Specific drop-out criteria include:

- Non-adherence to intervention: Failure to attend >3 consecutive structured exercise sessions (intervention arm) or $<85\%$ of total planned exercise sessions; failure to attend ≥ 2 intergenerational activity sessions or $<85\%$ overall attendance for SHP phase.
- Development of exclusion criteria during study: New onset of disability, suspected/confirmed dementia, depression (GDS-15 score indicating moderate-severe depression requiring intervention), total immobility, uncontrolled chronic disease, or hemodynamic instability.
- Acute illness or clinical worsening: Occurrence of acute conditions (e.g., pneumonia, acute arthritis with VAS $>6/10$, acute stroke, acute myocardial infarction, uncontrolled hypertension $\geq 180/100$ mmHg, acute COPD exacerbation) requiring hospitalization or prohibiting continuation.
- Adverse events suspected related to intervention: Intolerable or serious symptoms (e.g., persistent severe fatigue, muscle pain, dizziness, fall during exercise, significant emotional distress during intergenerational activities) leading to investigator decision for withdrawal.
- Voluntary withdrawal: Subject (or orphanage representative for children) requests discontinuation for any personal reason (e.g., lack of time, loss of motivation, transportation difficulties).
- Loss to follow-up: Inability to contact subject despite ≥ 3 attempts via phone/WhatsApp over 2 weeks, or permanent relocation outside study area.
- Death: Any mortality during study period (reported immediately as serious adverse event).

All drop-outs are documented in detail (date, reason, last completed assessment/procedure) on the case report form and in the trial master file.

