9. STATISTICAL ANALYSIS

All collected data will be initially recorded on research case report forms (CRFs) and subsequently transferred to secure electronic storage for data cleaning, coding, and verification. Descriptive data and analytical results will be presented in narrative text, tables, or figures as appropriate.

Normality of data distribution will be assessed using the Kolmogorov-Smirnov or Shapiro-Wilk test ($p > 0.05$ indicates normal distribution). Normally distributed continuous data will be presented as mean \pm standard deviation (SD); non-normally distributed data as median with minimum-maximum range. Categorical data will be presented as frequencies and percentages. Statistical significance will be set at $p < 0.05$. All analyses will be performed using SPSS version 20 software.

Primary analyses will be conducted on the per-protocol (PP) population, excluding drop-out subjects. Between-group comparisons of changes in study outcomes (hand grip strength, gait speed, MoCA-Ina score, serum mBDNF levels, and health-related quality of life) will use unpaired t-tests (parametric) or Mann-Whitney U tests (non-parametric), selected based on normality test results.

Correlations between serum mBDNF levels and MoCA-Ina score, hand grip strength, and gait speed will be evaluated using Pearson correlation (for normally distributed variables) or Spearman correlation (for non-normally distributed variables), according to normality assessment of each variable.

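### Participants who deteriorate on study become withdrawals or drop-outs, and section 9 excludes drop-outs, so they most likely leave the primary comparison

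*Combined protocol and SAP*

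**What the plan says.** Section 7.5 lists the grounds on which the investigator withdraws a participant. They include "Development of exclusion criteria (e.g., new disability, dementia suspicion, uncontrolled chronic disease", and "Acute illness requiring hospitalization or prohibiting continuation (e.g., pneumonia, acute stroke, uncontrolled hypertension", each closing a bracketed list of examples. They also include adverse events that cannot be tolerated and are suspected to come from the intervention. Section 5.3 likewise says that participants who deteriorate clinically or fall acutely ill are withdrawn and referred.

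Section 7.5.1 opens with a general rule: "Subjects are classified as drop-outs if they do not complete the study protocol through the final assessment (week 16) for any reason". It then lists specific drop-out criteria, among them new disability, "suspected/confirmed dementia, depression (GDS-15 score indicating moderate-severe depression requiring intervention), total immobility", uncontrolled chronic disease, and the acute illnesses above. Its adverse-event criterion ends with the examples "fall during exercise, significant emotional distress during intergenerational activities) leading to investigator decision for withdrawal".

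Section 9 defines the primary analysis set: "Primary analyses will be conducted on the per-protocol (PP) population, excluding drop-out subjects". It describes no intention-to-treat analysis. Section 3 says the reverse: "The trial follows intention-to-treat principles with per-protocol sensitivity analysis". Sections 7.5 and 7.7 encourage withdrawn participants to complete final assessments so that an intention-to-treat analysis can use them.

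On what the control arm does, section 5.1 says: "They will not participate in the structured exercise or SHP-based intergenerational activities during the study period".

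**The concern.** The grounds for removal overlap with what the trial measures. Suspected dementia is close to a poor MoCA-Ina score. New disability and immobility are close to poor gait speed, grip strength and CHS frailty status. Depression bears on the mental component of the SF-12. A participant who declines far enough is taken out of the comparison meant to detect decline, and this happens after randomisation.

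If more deteriorating controls than intervention participants are systematically removed, a real benefit shrinks. If more intervention participants are removed, for example after harm in a session, the benefit is inflated. Adverse events and drop-out reasons are still recorded, so harm stays in the trial record, but it can disappear from the efficacy comparison. The withdrawal ground of suspected dementia also has no threshold, and sections 3 and 7.2 describe the trial as open-label (section 5 says otherwise), so judgement enters the decision.

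**Working it through.** **1. Does the text remove these participants?** Sections 5.3 and 7.5 withdraw them, 7.5.1 lists their events as specific drop-out criteria, and section 9 excludes drop-outs. One step is a matter of reading. The opening sentence of 7.5.1 defines a drop-out as someone who does not complete the study protocol through week 16, so a withdrawn participant who attends week 16 might be argued to be in or out. Because the events are themselves named as criteria, 'out' is the more likely reading.

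**2. The plan's own numbers.** Section 4.5 gives a largest requirement of 42 per group (two-sided 5%, 80% power) and 50 per group randomised. Section 7.6 allows up to 15% drop-out. 42 / (1 − 0.15) = 49.4, rounded up to 50, which reproduces the plan's figure. The documents print no SD or mean difference. For a two-sample t-test, 42 per group at 80% power corresponds to a standardised difference of 0.619 (normal approximation 0.611). This serves only as a yardstick. The 15% is 0.15 × 50 = 7.5 per arm from all causes, and no rate is given for deterioration alone.

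**3. Shift per participant removed.** Let *k* of 50 in an arm be removed, and let them average *g* SD worse than those kept in that arm. The kept mean then exceeds the all-randomised mean by *k·g*/50. For removals *kt* (intervention) and *kc* (control):

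shift in the difference = (*kt* − *kc*)·*g* / 50

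The range *g* = 1 to 2 is an assumption; the documents give no figure.

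| Net systematic removal from one arm | Shift (SD) | Share of 0.619 |
|---|---|---|
| 0 | 0 | 0% |
| 1 | 0.02 to 0.04 | 3% to 6% |
| 2 | 0.04 to 0.08 | 6% to 13% |
| 4 | 0.08 to 0.16 | 13% to 26% |

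The sign follows the arm that loses more.

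**4. When the shift is a bias.** Suppose there is no effect and one removal rule acts identically in both arms. Kept participants then have the same distribution in each arm, however many each arm happens to lose. Simulating 50 per arm with assumed removal of 2%, 4% or 8% in both arms gives a false-positive rate of about 5%. A chance imbalance therefore does no harm to the error rate. If removal acts in one arm only, the rate does rise. With 4 removed from one arm, the standard error is √(1/46 + 1/50) = 0.204, and P(|Z + shift/0.204| > 1.96) is 6.8% for *g* = 1 and 12.3% for *g* = 2. Simulation of one-arm removal, which allows for the extra spread in the arm left intact, gives 6.6% to 10.5%.

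**5. Is systematic asymmetry supported?**
- Adverse events during exercise or intergenerational sessions: plausible, because only the intervention arm attends those sessions.
- Dementia, depression, disability and acute illness: only possible. Both arms have MoCA-Ina and GDS-15 at week 12 (7.4) and the same phone monitoring two to three times a month (5.2). The weekly pre-session checks (7.3.8) belong to the exercise phase and give the intervention arm some extra observation.

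**The case against.** The strongest reply is that this is one consequence of the conflict between sections 3 and 9. If section 3 governs, every collected value returns to the analysis. That is right, and the analysis part of the fix does restore section 3. But section 9 is the operative statistical text and describes no intention-to-treat analysis, so the conflict has to be resolved in writing.

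A second reply is that follow-up is already handled. Section 7.7 separates withdrawal from treatment from follow-up, 7.4 offers home visits, and the sentence in 7.5 that stops further procedures follows the one on voluntary withdrawal. This stands in part. Final assessments are still only encouraged, and nothing says that the visits stay scheduled after the investigator withdraws someone.

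A third reply is that section 7.1.1 names frailty and mBDNF as the main endpoints. Section 9's list of between-group comparisons omits frailty, and no link between these events and mBDNF is shown. The clearest links are to outcomes that 7.1.2 makes secondary. This limits the reach of the point, and no frailty figure is offered for that reason.

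A reader might infer that falls during exercise can occur only in the intervention arm. The documents do not support that. Controls receive e-flyers that include physical activity advice and continue their routine community activities. The asymmetry concerns events in trial sessions, and sections 6.4 and 12.1 rate the fall risk as low.

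**Conclusion.** The point stands as a should-fix matter, with medium confidence. Following section 9 as written most likely takes participants who deteriorate out of the primary comparison, and so selects on post-randomisation states tied to MoCA-Ina, gait speed, grip strength, SF-12 and frailty.

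Two stronger readings are tempting and unsupported. One is that the result will be biased, or biased in favour of the intervention. The documents give neither event rates nor the direction of any imbalance; balanced removals with equal deficits give no shift, and systematic loss from the control arm works against the intervention. The other is that any imbalance in the number removed raises the false-positive rate. It does not when one common rule applies to both arms; only a systematic difference in removal or detection does.

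The size is unknown. The 0.02 to 0.04 SD per net participant rests on 50 per arm, an assumed deficit of 1 to 2 SD, and removal that differs systematically by arm. The 0.62 SD yardstick is the smallest standardised difference implied by section 4.5; outcomes that need fewer participants imply larger ones, against which the same shift matters less.

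**What to change.** 1. In 5.3, 7.5 and 7.5.1, state that new disability, suspected dementia, depression, total immobility, uncontrolled disease, acute illness and intolerable adverse events may stop trial sessions on clinical grounds, but do not end follow-up or make someone a drop-out.
2. Keep the week-12 and week-16 assessments scheduled for participants whom the investigator withdraws, unless they withdraw consent, using the home visits in 7.4.
3. In section 9, make the primary comparison all randomised participants as assigned, using all collected values, with per-protocol as the sensitivity analysis, as section 3 already says.

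The cost is protocol wording and a few visits that are harder to complete, of a kind already planned. Group means may look less favourable, because participants who did badly are counted.
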